### Serious Adverse Events (SAEs)

An SAE is defined as any untoward medical occurrence that:

- Results in death
- Is life-threatening
- Requires inpatient hospitalization or prolongation of existing hospitalization
- Results in persistent or significant disability/incapacity
- Is a congenital anomaly/birth defect

- Is an important medical event that may not be immediately life-threatening or result in death or hospitalization but may jeopardize the patient or may require intervention to prevent one of the other outcomes listed in the definition above).

### Reporting Requirements

Adverse events must be reported by study personnel into the Redcap system using the electronic case report forms within 3 days of their knowledge of the occurrence. Investigators are responsible for following all relevant local IRB policies and procedures. The Principal Investigator will follow IRB policy in terms of reporting adverse events.

Serious Adverse Events that occur within 6 weeks after randomization must be reported by the site investigator or personnel into the Redcap system on the Serious Adverse Event CRF within 1 working day after the site investigator or personnel first learn of the event.

For SAEs, the Principal Investigator will review the report and obtain any needed additional clarifications concerning the event by direct telephone conversations and/or e-mail with the involved providers. The investigator's description and categorization of the event, and additional relevant information, will then be reviewed by the study's Safety Officer. The Safety Officer will determine if the event was properly categorized. If not, he will provide the Principal Investigator with a modified categorization, along with a brief written rationale for re-categorizing the event. In nearly all instances, the Safety Officer's categorization will be considered the final categorization of the event.

### Expedited Reporting

Events meeting criteria as an unanticipated problem (UP) or unexpected adverse drug event (UADE) will be reported to the IRB within 10 working days of becoming aware of the event. If the event results in death, it will be reported within 1 working day of becoming aware of the event.

All other events that do not meet criteria as a UP or UADE will be reported to WUSTL IRB at the time of continuing review

### **Independent Data and Safety Monitoring Board (IDSMB)**

An IDSMB consisting of members who are independent from the Sponsor will be established. The IDSMB will have at least 3 members. The IDSMB will be responsible for reviewing outcomes and AEs. The first IDSMB meeting will be held after approximately 100 participants have completed treatment. The frequency of subsequent meetings will be decided by the IDSMB, but will be not less than every 3 months. The IDSMB may also meet in *ad hoc* meetings at its discretion as needed in response to events occurring in the trial. Additional responsibilities for the Committee include confirmation of the safety and appropriateness of the selected dosing regimen. After each meeting, the IDSMB will recommend that the study can continue, or may recommend changes to the study or stopping the study. Details of the membership and responsibilities of the IDSMB will be included in the IDSMB Charter.

The IDSMB will also monitor new developments in COVID-19 research and treatment, and factor any related ethical considerations into its determinations as to whether or not the study should be terminated for futility for one.

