### **Exploratory**

1. COVID-19 specific mortality
2. Number of patients with diagnosed cardiomyopathy
3. Number of patients with new onset arrhythmia

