## SUBJECT EXCLUSION CRITERIA

- Contraindication or allergy to chloroquine, hydroxychloroquine or azithromycin
- Current use hydroxychloroquine, chloroquine or azithromycin
- Concurrent use of another investigational agent
- Invasive mechanical ventilation
- Participants who have any severe and/or uncontrolled medical conditions such as:
  - unstable angina pectoris,
  - symptomatic congestive heart failure,
  - myocardial infarction,
  - cardiac arrhythmias or know prolonged QTc  $>470$  males,  $>480$  female on ECG
  - pulmonary insufficiency,
  - epilepsy (interaction with chloroquine),
- Prior retinal eye disease
- Concurrent malignancy requiring chemotherapy
- Known Chronic Kidney disease, eGFR $<30$  or dialysis
- G-6-PD deficiency, if unknown requires G6PD testing prior to enrollment
- Known Porphyria
- Known myasthenia gravis
- Currently pregnant or planning on getting pregnant while on study
- Breast feeding
- AST/ALT  $>$  five times the upper limit of normal ULN\*
- Bilirubin  $>$  five times the ULN\*
- Magnesium  $<1.4$  mEq/L\*
- Calcium  $<8.4$  mg/dL  $>10.6$  mg/dL\*
- Potassium  $<3.5$   $>5.5$  mEq/L\*
- Current concomitant use of contraindicated drugs including antiarrhythmics, antidepressant, anticonvulsants (see Appendix 2 for full list)

\*Patients who do not meet laboratory criteria may be rescreened within 48 hrs.

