Nervous system disorders: Convulsions, mild and transient headache, polyneuropathy, acute extrapyramidal disorders (such as dystonia, dyskinesia, tongue protrusion, torticollis).

Neuropsychiatric disorders: Neuropsychiatric changes including psychosis, delirium, anxiety, agitation, insomnia, confusion, hallucinations, personality changes, depression, and suicidal behavior.

Cardiac disorders: Hypotension, electrocardiographic changes (particularly, inversion or depression of the T-wave with widening of the QRS complex), and cardiomyopathy (which may result in cardiac failure and in some cases a fatal outcome).

Cardiac arrhythmias, conduction disorders such as bundle branch block / atrio-ventricular block, QT interval prolongation, torsade de pointes, ventricular tachycardia and ventricular fibrillation have been reported with therapeutic doses of Chloroquine as well as with overdose. The risk is greater if Chloroquine is administered at high doses. Fatal cases have been reported.

Metabolic and Nutritional disorders: Hypoglycemia.

Risk of overdose: Chloroquine is very rapidly and completely absorbed after ingestion. Toxic doses of Chloroquine can be fatal. As little as 1 g may be fatal in children. Toxic symptoms can occur within minutes. The symptoms of overdosage may include nausea, vomiting, headache, drowsiness, visual disturbances, cardiovascular collapse, convulsions, hypokalemia, rhythm and conduction disorders including QT prolongation, torsades de pointes, ventricular tachycardia and ventricular fibrillation, followed by sudden potentially fatal respiratory and cardiac arrest. Immediate medical attention is required, as these effects may appear shortly after the overdose. Cases of extrapyramidal disorders have also been reported in the context of Chloroquine overdose.

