## **STUDY PROCEDURES**

### **Schedule of events**

	Screen (using SOC in last 48hr	Baseline Screening and baseline may be combined if labs are done								Weeks		
Week		1	1	1	1	1	1	1-2	3	4	5	6
Day		0	1	2	3	4	5	6- 14	21	28	35	42
Window (hrs) +/-				6	6	6	6	24	48	48	48	48
Informed consent	x											
SARS CoV-2	x											
EKG	x											
Medication review	x											
Complete blood count, comprehensive metabolic panel and magnesium	x											
History of Glucose- 6 phosphate- dehydrogenase	x											

(G6PD) deficiency assessment												
(G6PD) lab (*research if preformed)	x*											
Determine eligibility		x										
Pregnancy test Unless SOC within 7-14 days	x											
Study drug		x	x	x	x	x	x					
Review medical record**	x	x	x	x	x	x	x	x	x	x	x	x
Adverse Drug Reaction Collection			x	x	x	x	x	x	x	x	x	x
Symptom screen		x	x	x	x	x	x	x	x	x	x	x
Temperature ( from medical record taken and recorded by participant while at home*)		x	x*	x*	x*	x*	x*	x*				

\* thermometer at home and log

\*\* medical history, study outcomes, AEs, SAEs

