### Eligibility

Participants hospitalized with SARS CoV-2 infection who meet the inclusion/exclusion criterion will be enrolled. Standard of care investigations including laboratory test (complete blood count, comprehensive metabolic panel, magnesium, and glucose-6-phosphate dehydrogenase) and ECG performed within 48 hours will be used to determine study eligibility.

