### Adverse Event Collection Requirements for this protocol

All AEs must be recorded on the eCRFs if any of the following criteria have been met.

- All Grade  $\geq 2$  AEs
- All AEs that led to a change in study treatment regardless of grade
- All AEs meeting SAE definition
- Started within 7 days after the last dose of study drug

All AEs that are reported must have their severity graded. To grade AEs, refer to the Division of AIDS Table for Grading the Severity of Adult and Pediatric Adverse Events (DAIDS AE Grading Table), corrected Version 2.1, July 2017.

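### No ECG or electrolyte result after screening is scheduled or named as study data, so arrhythmia counts can reflect how closely each open-label arm was observed, and nothing recorded would show it

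*Combined protocol and SAP*

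**What the plan says.** - **Entry.** The exclusion criteria list "cardiac arrhythmias or know prolonged QTc", with limits of 470 for men and 480 for women, and also set limits on magnesium, calcium and potassium. These apply to all four arms.
- **Stated risk.** The section on risks of chloroquine says that QT prolongation, torsade, ventricular tachycardia and ventricular fibrillation "have been reported with therapeutic doses of Chloroquine as well as with overdose", and that some cases were fatal.
- **Schedule.** In the Schedule of events, the EKG row and the row for blood count, metabolic panel and magnesium each carry one mark, in the screening column. The Eligibility section gives these tests a single use: "ECG performed within 48 hours will be used to determine study eligibility".
- **After baseline.** Record review is marked at every time point to Day 42, for "medical history, study outcomes, AEs, SAEs". Adverse events go on the eCRF if they meet any one of several criteria, such as Grade 2 or higher, or "Started within 7 days after the last dose of study drug".
- **Endpoint.** The third exploratory endpoint is "Number of patients with new onset arrhythmia". It has no definition, data source or time window. The analysis section allows survival methods, t-tests, chi-square or Fisher's exact tests, as appropriate.
- **Monitoring.** The IDSMB reviews outcomes and adverse events, and its duties include "confirmation of the safety and appropriateness of the selected dosing regimen". On timing: "The first IDSMB meeting will be held after approximately 100 participants have completed treatment". Further detail is left to a charter that is not among the documents.

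**The concern.** The plan treats QTc and electrolytes as important enough to bar entry, then names no such value as study data once dosing starts. What it learns about cardiac rhythm depends on what the treating teams order and chart, and those teams know the allocation.

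Two things are at stake. First, a comparison of arrhythmia counts mixes true risk with intensity of looking. Without a record of who had an ECG or telemetry, a low count may mean few arrhythmias or few ECGs. Second, the IDSMB is asked to confirm that the regimen is safe, but the protocol does not specify that it will see any on-treatment QTc value, or how many patients had one.

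Observation time may also differ. The sample-size section assumes median recovery of 7 days with azithromycin and 11 days without. If discharge follows recovery, the arms would differ in days under inpatient observation under the plan's own hypothesis. The Enrollment section also provides for finishing the drug course after discharge.

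**Working it through.** **No planned figure to reproduce.** The documents give no arrhythmia rate, ECG-use rate or power for this endpoint. The 82% power in the sample-size section concerns time to recovery and does not bear on this point.

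**Step 1: the scheduled data.** Post-dose ECGs or electrolyte tests scheduled per participant: 0, for all 500. At the first IDSMB meeting about 100 / 4 = 25 participants per arm will have completed treatment, with no QTc value after first dose specified for any of them.

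**Step 2: what unequal detection does.** Let r be the true proportion with new-onset arrhythmia, equal in two arms, and let d1 and d2 be the proportions of those cases that are detected and charted. The expected observed proportions are r × d1 and r × d2, so the apparent ratio is d1 / d2 whatever the value of r.

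**Step 3: size under assumptions.** Take d1 = 80% and d2 = 50% (assumed), so the apparent ratio is 0.80 / 0.50 = 1.6. With 125 per arm, expected cases are 125 × r × d. Rejection rates come from enumerating both binomial distributions and applying a two-sided Fisher test at 0.05.

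| Assumed true rate, both arms | Expected cases, 80% detection | Expected cases, 50% detection | Fisher rejects |
|---|---|---|---|
| 2% | 2.0 | 1.25 | 0.5% |
| 5% | 5.0 | 3.125 | 4.2% |
| 10% | 10.0 | 6.25 | 9.8% |

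For reference, with 50% detection in both arms and a 10% true rate, the test rejects in 2.2% of trials.

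**Step 4: range over other splits, true rate 10%.** Detection of 40% v 60% gives 5.0 v 7.5 expected cases, a ratio of 1.5 and rejection in 5.8% of trials. Detection of 30% v 70% gives 3.75 v 8.75 cases, a ratio of 2.33 and rejection in 19.8%.

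**Step 5: the first IDSMB look.** With 25 per arm and a 5% true rate, expected detected cases are 25 × 0.05 × 0.50 = 0.6 or 25 × 0.05 × 0.80 = 1.0 per arm. Counts that small say little about the regimen, and less still if the number of patients examined is unknown.

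**Step 6: direction.** The documents fix no direction. More ECGs in an arm raise its count; earlier discharge lowers it. The comparison can be affected between chloroquine and hydroxychloroquine as well as by azithromycin.

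**The case against.** The strongest reply is that cardiac events are not lost. Record review runs to Day 42 for study outcomes, and new-onset arrhythmia is one of them. An adverse event includes any unfavorable sign, abnormal laboratory findings among them, and Grade 2 or higher must be recorded. Serious events are entered within 1 working day and reviewed by the Safety Officer. This stands: a reader might infer that no ECG information reaches the trial after screening, and that is not so. It does not close the gap, because these routes capture abnormal findings and not the number of patients examined.

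A reader might also infer that the azithromycin arms will be examined more and will show a spurious excess. The documents do not support that. They tie QT prolongation to chloroquine, list no QT or arrhythmia risk for azithromycin, and apply the QTc limit to all arms. Nothing in them shows that ECG use will differ by arm.

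A third tempting inference is that the IDSMB cannot do its task. That is not shown: it sees outcomes and adverse events, may meet ad hoc, and works under a charter that is not before us. Nor do the documents say that confirming the regimen requires serial QTc values.

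It is also fair to say that an entry rule, a risk disclosure and an exploratory count do not strictly contradict one another, that relying on standard-of-care ECGs is a design choice, and that the endpoint lies outside the primary hypotheses. At the assumed 80% v 50% split, the expected result at a 10% true rate is about 10 v 6 cases, with a Fisher p-value of 0.44. This limits the weight of the point without removing it.

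**Conclusion.** The point holds in limited form. No ECG or electrolyte test is scheduled after screening, no such value is a named data item, and the plan records nothing that would show whether arrhythmia counts differ because of risk or because of observation. That the counts can reflect ECG use is established; that they will is not.

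The size rests wholly on assumed detection and event rates. At 80% v 50% detection the apparent ratio is 1.6, while the chance of a false significant result stays between about 0.5% and 10% for true rates of 2% to 10%. It rises further only with wider splits or higher true rates. The main cost is therefore counts that cannot be interpreted, more than false significance. Deaths and overt serious arrhythmias are less affected, and the primary endpoint is untouched. This is a cheap improvement worth making before the first IDSMB review.

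**What to change.** Without adding any procedure:

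1. In the record reviews already scheduled, abstract every standard-of-care ECG from first dose through the hospital stay (date, QTc, rhythm), telemetry use, and potassium and magnesium results.
2. Give the IDSMB, by arm, QTc change from the screening ECG together with the number and percentage of patients with at least one post-dose ECG.
3. In the analysis of secondary and exploratory endpoints, report new-onset arrhythmia beside ECG and telemetry frequency by arm, and state that the comparison depends on ascertainment.
4. Do not test arrhythmia again only in patients with a post-dose ECG, or label that table descriptive. Having an ECG is decided after randomization and may depend on arm and symptoms, so the restriction can add selection bias.

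The cost is extra eCRF fields, abstraction time and IDSMB table shells. QTc change will exist only for patients who happened to have an ECG, which is why coverage must be shown with it.

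Whether on-treatment ECGs should be required is a clinical decision for the sponsor when reconciling the exclusion criteria, the chloroquine risk text, the schedule, the arrhythmia endpoint and the IDSMB's task.

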## **STATISTICAL CONSIDERATIONS**

The proposed study is a 4-arm parallel group, open-label randomized clinical trial. The treatment arms, hydroxychloroquine alone (HCQ), hydroxychloroquine + azithromycin (HCQ + AZM), chloroquine alone (CQ) and chloroquine + azithromycin (CQ + AZM) will be randomly assigned eligible participants. The primary hypotheses in this study are whether the addition of AZM to either HCQ or CQ improve patient recovery rates.

#### *Primary endpoint analysis*

The primary endpoint of this study is the time to recovery following the definition outlined in the STUDY AIMS/ENDPOINTS section. Our primary analysis will be to use Kaplan-Meier (KM) survival analysis to test the statistical null hypothesis that there is no difference in recovery rates between the non-AZM treatment arms and the AZM treatment arms (HCQ vs HCQ + AZM, CQ vs CQ + AZM). If either of the AZM arms have significantly faster recovery rates (two-sided  $P$ -value  $< 0.05$ ) compared to the corresponding non-AZM arm group, then we will conclude that the AZM group is superior to the non-AZM group. We will also compare recovery rates between the HCQ vs CQ, and HCQ + AZM vs CQ + AZM treatment arms to assess whether HCQ and CQ treatments differentially influence recovery. We will then proceed to a multivariable Cox-regression model that adjusts symptom severity at baseline (sum of presence of fever  $\geq 38.0^{\circ}\text{C}$  and total number of 'Quite a Bit' or 'Very much' responses to the Flu-PRO questionnaire [maximum total = 20]). The final model will retain the treatment groups and those covariates that are significant ( $P < 0.05$ ) in the multivariable model and we will report the model-adjusted hazard ratios and 95% CI for the treatment groups as well as the covariates. Participants that are lost to follow-up or die will be censored at the date of last contact or date of death, respectively, and patients that do not recover during the study period will be censored at 42 days. The primary analysis will be intention-to-treat and a per-protocol analysis will also be performed as a secondary analysis of the primary endpoint. Statistical analyses will be conducted using PROC LIFETEST and PROC PHREG as appropriate (SAS Institute Inc, Cary, NC, USA).

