### **RANDOMIZATION PROCEDURES**

Randomization will be performed by the BJH Investigational Drug Service (IDS) using a computer-generated randomization sequence, which will be concealed from investigators and the research team through study completion. Consented patients will be randomly assigned to one of four open-label treatment cohorts in a 1:1:1:1 ratio using permutation blocks (block size will be determined by the study statistician). Medications will be prepared and dispensed by the IDS pharmacy and delivered to the appropriate coordinator. The research pharmacy will maintain randomization, dispensing, and accountability logs. All medications will be stored in a

secure location within the research pharmacy and maintained under controlled environmental conditions.

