### Baseline assessment

Eligible participants will be consented and randomized according to the procedure outlined above. Demographics and clinical parameters will be recorded

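### Cheap improvement, not an error: superiority is decided on an unadjusted comparison although a severity-adjusted Cox model is already planned (assumed gain about 0 to 5 power points for weak to moderate severity effects)

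*Combined protocol and SAP*

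**What the plan says.** In Primary endpoint analysis, the decision rests on the following: "Our primary analysis will be to use Kaplan-Meier (KM) survival analysis to test the statistical null hypothesis" of no difference between each azithromycin arm and its partner without azithromycin. Superiority is concluded if the two-sided P value is below 0.05. No covariate or stratum is named for this test. The plan does not use the words log-rank or unadjusted; that reading follows from Kaplan-Meier with PROC LIFETEST and no strata.

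Only then comes the adjusted model: "We will then proceed to a multivariable Cox-regression model that adjusts symptom severity at baseline". Severity is a score that adds fever at entry to the number of Flu-PRO symptoms given one of the two highest ratings, up to 20. Of this model the plan says "The final model will retain the treatment groups and those covariates that are significant" at P<0.05. It supplies hazard ratios and confidence intervals, not the conclusion.

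Randomization Procedures assigns patients "in a 1:1:1:1 ratio using permutation blocks" and names no stratification factor.

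On timing, the Baseline assessment section reads in full: "Eligible participants will be consented and randomized according to the procedure outlined above. Demographics and clinical parameters will be recorded". The Schedule of events lists "Symptom screen" on day 0, in the same column as study drug. The Follow up section counts the surveys from randomization. Statistical Considerations describes the trial as open-label.

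**The concern.** Recovery requires that fever has gone, that no symptom is worse than mild and that no extra oxygen is needed. A patient who enters with fever and many severe symptoms has further to go than one who enters with few, and the inclusion criteria set no minimum for either. Baseline severity is therefore a plausible predictor of time to recovery, and the plan already treats it as worth adjusting for.

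In a proportional hazards setting, leaving out a predictor pulls the estimated treatment effect towards no effect and costs power. Naming the covariate in advance for the deciding test recovers that power without more participants. It also settles which hazard ratio is reported, which the P<0.05 rule leaves to the data.

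**Working it through.** **1. Reproduce the planned power.** Inputs from Sample size and power analysis: medians of 11 and 7 days, 125 per arm, censoring 0.04 per day, two-sided α 0.05. The 42-day cut-off is from Primary endpoint analysis. Exponential times are assumed.

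- Hazards: ln2/11 = 0.0630 and ln2/7 = 0.0990; ratio 11/7 = 1.571.
- P(event) = λ/(λ+0.04) × [1 − exp(−(λ+0.04)×42)] = 0.604 and 0.710.
- Events: 125 × (0.604 + 0.710) ≈ 164.2.
- Power (Schoenfeld): Φ(√164.2/2 × ln 1.571 − 1.96) = Φ(2.896 − 1.960) = Φ(0.936) = 82.5%. Simulation of the log-rank test gives 81.7%. The plan states 82%.

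**2. Effect of adjusting for severity alone.** The documents give no covariate effect, so each hazard ratio (HR) of recovery per SD of severity below is an assumption. The conditional treatment HR is held at 11/7, with the same censoring and cut-off. The table shows 20,000 trials per row with a normally distributed score and model-based variance.

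| HR per SD | Log-rank | Adjusted Cox | Difference |
|---|---|---|---|
| 1.00 | 81.7% | 81.6% | −0.1 |
| 0.82 | 79.8% | 81.4% | +1.6 |
| 0.74 | 77.9% | 81.3% | +3.4 |
| 0.67 | 74.5% | 81.0% | +6.5 |
| 0.61 | 70.6% | 80.2% | +9.6 |

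(0.82, 0.74, 0.67 and 0.61 are the inverses of 1.22, 1.35, 1.49 and 1.65.)

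A run with a skewed 0–20 count score (6,000 trials, robust variance) gave 81.6% vs 82.7% at HR 0.86, 76.9% vs 81.2% at 0.74, and 70.8% vs 80.9% at 0.61. A third run (3,000 trials, model-based variance) gave 81.1% vs 80.7% with no effect, then 81.3% vs 81.8%, 77.6% vs 80.9% and 71.3% vs 81.0% at the same three HRs. Up to HR 0.74 the differences run from −0.4 to +4.3 points.

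**3. Dependence on how the planned effect is read.** In step 2 the gap opens because the log-rank test loses power; the adjusted test stays near 80–82%. Two other readings:

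- The treatment effect is raised so that the log-rank test keeps about 82–84%: gains of 1.4, 3.1 and 5.2 points at HR 0.82, 0.74 and 0.67.
- The two planned exponential curves are kept exactly (6,000 trials; severity and oxygen need both in the model, robust variance): 81.8% vs 82.2% (weak), 83.1% vs 84.1% (moderate), 81.9% vs 87.0% (strong). For weak to moderate effects that is 0.4 to 1.0 points, and up to 1 point of the robust test's power reflects its slightly higher type I error.

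**4. Cost if severity does not matter.** The loss is 0.1 and 0.4 points in the runs above. It is 1.0 point (81.7% vs 80.7%) with model-based variance when the model is also stratified by oxygen need.

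**5. Type I error.** In the 20,000-trial runs it was 5.2–5.4% unadjusted and 5.1–5.3% adjusted; in the 3,000-trial runs it was 4.3–5.6% across both tests. If the severity effect stops at day 7 (HR 0.74, 0.61, 0.50; oxygen HR 0.5 also assumed), model-based variance gives 5.1%, 5.4% and 5.7%, and robust variance 5.3%, 5.3% and 5.5% (Monte Carlo error 0.2).

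**6. Timing of the score.** Suppose the score is given after allocation is known and one arm reports it 0.2 SD lower. With severity and oxygen in the model, the adjusted test's type I error is 7.3% (moderate effects) or 10.2% (strong effects). The log-rank test gave 5.6% and 5.5% in the same runs.

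**The case against.** An unadjusted deciding test with an adjusted supportive model is common and valid, and the plan already reports the adjusted hazard ratio. No document shows that power is being lost, and with the planned curves kept exactly there is no clear gain for weak to moderate effects. All of this stands, and it limits the point to an improvement.

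The P<0.05 retention rule also does little damage where adjustment matters: severity was kept in about 95% of simulated trials at HR 0.74. Where the rule is erratic (kept in 45% of two-arm models in the weak case), there is little to gain. The reason to drop it is that a deciding test needs a fixed model.

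The timing objection is the most serious. The present test does not use the self-reported baseline score and so is not exposed to the bias in step 6. Scoring before randomization is therefore a condition of the change.

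Stratifying by oxygen need at entry would rest on an assumed 50% prevalence, assumed effects and an item that the Baseline assessment section does not name. Robust variance shows no clear advantage in step 5. Neither belongs in the core proposal.

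A reader might infer that the trial is underpowered, or that its primary test is wrong. The documents support neither. The 82% reproduces, and the lower log-rank figures in step 2 come from covariate effects that were assumed, not from anything the plan states.

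**Conclusion.** The point holds as a low-cost improvement. The deciding test is valid and has the power claimed for it under the plan's own assumptions. Using the severity score already defined would gain about 0 to 5 power points if severity is weakly to moderately prognostic (HR per SD down to about 0.74), and about 1 point or less if the planned curves are kept exactly. It gains roughly 10 points only if severity is strongly prognostic (HR about 0.61) and the conditional treatment effect stays at 11/7. If severity is not prognostic, the cost is about 1 point at most.

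These sizes rest on assumed covariate effects and score distributions and on proportional hazards. The gain is safe only if the score is taken before allocation is known. Testing two azithromycin comparisons, each at 0.05, is a separate matter.

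**What to change.** In Primary endpoint analysis, delete the P<0.05 retention rule and state:

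> For each azithromycin comparison, the deciding test is the two-sided test of treatment in a Cox model containing treatment and the baseline symptom severity score, which is kept whatever its P value. The hazard ratio is conditional on severity. The log-rank test and Kaplan-Meier curves are supportive. A score recorded only after randomization counts as missing, and missing scores are replaced by the median pooled across arms.

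In Baseline assessment, state that the severity score is completed before randomization. If most scores cannot be obtained by then, keep the log-rank test as the deciding test. The pre-randomization rule is worth adopting in any case, because the Cox model already planned uses the same score.

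Optional: oxygen need at entry over the patient's usual level may be a second prespecified factor if it is recorded before randomization. Robust variance may be used but is not needed.

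The change needs no additional participants. It costs plan wording and one fixed time of collection, settled before any comparison of outcomes by arm. The Sensitivity analyses section compares against the primary analysis, so it should then refer to the adjusted model. Downsides: the hazard ratio becomes conditional, the model assumes proportional hazards, and a missing-score rule is needed. That rule was checked at 15% missing, with moderate effects and oxygen also in the model: power 75.8% unadjusted vs 80.2% adjusted, type I error 5.2%. Larger shares of missing scores were not examined.
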